development of a robust, clinically feasible rsfMRI data analysis pipeline, this study is expected to result in improved understanding of the functional reorganization that takes place during and after intervention.

4. Study Procedures

- Study design, including the sequence and timing of study procedures (distinguish research procedures from those that are part of routine care).

This will be an early phase 1 (phase 0) clinical trial. Specifically, the study will be performed as a randomized, parallel group trial to determine if the amount of changes in brain functional connectivity outcome measures (i.e., between network connectivity) is significantly different between the group of patients that perform FES cycling and another group of patients that perform passive (sham) cycling.

Patients of the International Center for Spinal Cord Injury (ICSCI) at the Kennedy Krieger Institute (KKI) will be identified as meeting the inclusion criteria by reviewing the medical records held by the ICSCI. Once the patient consents by signing the consent form, official screening of subjects will be performed. Subjects will be randomized into 2 groups: FES cycling (Group 1; n=24) and passive cycling (Group 2; n=24). The patients will undergo either an FES cycling or a passive cycling sessions for 4 weeks, 3 times a week. **Acquisition of rsfMRI measures:** MRI will be performed on all participants at the beginning (prior to cycling sessions) and at the end of the 2nd and 4th weeks of the intervention program. **Acquisition of clinical measures:** ISNCSCI and SCIM (Spinal Cord Independence Measure) evaluations will be performed to coincide with the dates of MRI acquisitions, to determine the neurological level and the degree of sensory and motor impairments. Detailed study timeline can be found in Figure 1.

[figure not shown]

Figure 1. Study Timeline.

- SCI patients assigned to FES cycling group will take part in the following evaluations:
 - Medical chart review / MRI screening questionnaire
 - FES cycling trial
 - Neurological evaluation (ISNCSCI – more commonly known as ASIA exam)
 - Functional evaluation (SCIM)
 - MRI

Date: 4.14.2023

Principal Investigator: [name].

Application Number: IRB000182576

E1: FES cycling

- SCI patients assigned to passive cycling group will take part in the following evaluations:
 - A: Medical chart review / MRI screening questionnaire
 - B2: Passive cycling trial

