- c. Justification and safety information if non-FDA approved drugs without an IND will be administered.

Date: 4.14.2023

Principal Investigator: [name].

Application Number: IRB000182576

N/A

7. Study Statistics

a. Primary outcome variable.

Type	Name	Time Frame	Brief Description
Primary	International Standard of Neurological Classification for Spinal Cord Injury (ISNCSCI)	baseline, mid-intervention, post-intervention	Developed by the American Spinal Injury Association (ASIA) as a universal classification tool for spinal cord injury (SCI). The classification tool involves a sensory and motor examination to determine the neurological level of the injury and whether the injury is complete or incomplete. The tool also provides sensory and motor scores of upper and lower body, as well as right and left of the body. The ISNCSCI defines neurological level as the most caudal level at which sensory and motor function are intact. The completeness of the injury is graded according to the ASIA Impairment Scale (ISNCSCI).
Primary	Resting state fMRI functional connectivity	Baseline, mid-intervention, post-intervention	RsfMRI functional connectivity is defined as the temporal dependency of neuronal activation patterns (represented by the blood oxygenation level dependent (BOLD) signal time courses as measured using rsfMRI) of anatomically separated brain regions. There are number of methodologies one can use to characterize the degree and type of rsfMRI functional connectivity. One example is between-network-connectivity (BNC), which is defined as the degree of correlation between two time courses obtained from a pair of brain regions. Summary statistics of BNC (e.g., mean, variance), as well as the dynamic properties of BNC (e.g., dynamic functional connectivity) can be used to further summarize the characteristics of the functional connectivity in SCI population.
Primary	RsfMRI brain parcels	Baseline, mid-intervention, post-intervention	RsfMRI functional connectivity can also be used to identify functionally homogeneous brain regions, or parcels of the brain. The parcels' center of mass, spatial maps, average and variance of the BOLD signal time courses within the parcels can be used to characterize brain functional organization.

b. Secondary outcome variables.

Type	Name	Time Frame	Brief Description

Date: 4.14.2023

Principal Investigator: [name].

Application Number: IRB000182576

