The spatial maps of ICA- and SCA-derived brain parcels will be compared across groups. First, the participant-specific sensory and motor brain parcels will be converted to z values, so image intensities reflect the degree to which the parcel is present in each participant's data. The brain parcels will be combined in a second-level random effects analysis using a two sample t-test in SPM8. Voxels that contributed unequally to the parcels across groups will be identified using a liberal voxel-wise p value of 0.01 and a cluster-level p value of 0.05 corrected for multiple comparisons². The between network connectivity (BNC) between sensory and motor parcels will be calculated using Pearson's correlation coefficient between pairs of participant specific motor and sensory brain parcels³. Pairwise-correlations will be converted to Z-scores using Fisher's transformation, and the BNC across groups will be compared using two-sample t tests and adjusted p-values using a false discovery rate correction. Next, we will investigate whether sensory and motor BNC measured at week 2 of cycling program are related to motor and sensory International Standards for Neurological Classification of Spinal Cord Injury (ISNCSCI) scores measured at week 4, using a multivariate linear regression model analysis. Finally, the longitudinal inter- and intra-subject reproducibility of the ICA- and SCA-derived brain parcels will be assessed using intra-class correlation coefficient (ICC).

d. Early stopping rules.

[figure not shown]

Figure 2. Correlations between sensorimotor-visual BNC measurements and total ISNCSCI scores in SCI patients suggest a compensatory plastic cortical changes that are related to clinical presentation of the patients. Patients with lower ISNCSCI score showed larger degree of functional connectivity between the sensorimotor and visual networks.

Date: 4.14.2023

Principal Investigator: [name].

Application Number: IRB000182576

The principal investigator may discontinue the study if the interim statistical analysis as described above indicates that the number of subjects required for this trial exceeds 50.

Patients may withdraw from the study at any time for any reason. Any investigator may discontinue a patient for any of the following reasons:

- The subject experiences a medical emergency that necessitates discontinuation of therapy

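### Parcel maps are tested at a voxel threshold of 0.01; if the cluster correction is parametric, its 5% error rate depends on a spatial correlation shape the plan does not give

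*Combined protocol and SAP*

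**What the plan says.** Section 7c opens its analysis paragraph with "The spatial maps of ICA- and SCA-derived brain parcels will be compared across groups". The sensory and motor parcels are converted to z values and enter a "second-level random effects analysis using a two sample t-test in SPM8". Voxels that differ between arms are then identified "using a liberal voxel-wise p value of 0.01 and a cluster-level p value of 0.05 corrected for multiple comparisons". The correction method is left to a footnote whose reference is not in the text reviewed. The section states no sidedness, smoothness, search volume, visit or adjustment across maps for this comparison.

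Section 7a lists brain parcels with type Primary; its description begins "RsfMRI functional connectivity can also be used to identify functionally homogeneous brain regions, or parcels of the brain" and includes spatial maps among the features that can be used. Section 4 randomises 24 participants to each arm and gives the imaging schedule: "MRI will be performed on all participants at the beginning (prior to cycling sessions) and at the end of the 2nd and 4th weeks".

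**The concern.** A parametric cluster p-value rests on approximations that work best with a high cluster-forming threshold and spatial correlation that dies off quickly, as a Gaussian shape does. A voxel threshold of 0.01, which the plan itself calls liberal, is low for this purpose. It lets through large connected clusters, and how large they grow by chance then depends on the tail of the spatial correlation. If that tail is long, a cluster reported at 5% could be a false positive much more often than 1 time in 20. At stake is whether a region reported as reorganised between arms, on an outcome labelled primary, carries the error rate the plan states.

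**Working it through.** **Inputs from the documents.** Voxel p 0.01 and cluster p 0.05 (Section 7c); 24 per arm (Section 4), so 24 + 24 - 2 = 46 degrees of freedom; 2 parcellation methods x 2 networks = 4 maps (Section 7c); 3 visits (Section 4).

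**Not in the documents.** Correction method, voxel size, smoothness, search volume, spatial correlation shape and sidedness. The plan's 5% therefore cannot be reproduced from its own figures. It can only be tested under stated assumptions.

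**Step 1: the parametric p-value.** For a largest cluster of k voxels in three dimensions,

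p = 1 - exp(-E[m] x exp(-b x k^(2/3))), with b = (Gamma(5/2) / E[n])^(2/3),

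where E[m] is the expected number of clusters above the threshold and E[n] the expected cluster size. Both are derived from smoothness estimated on the residuals.

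**Step 2: false-positive rate on null maps, 24 v 24, one-sided, per map.** Simulation A: 32 x 32 x 32 voxels, smoothness about 3 voxels, about 370 replicates, two Gaussian-plus-exponential mixtures for the long tail. Simulation B: 3 mm voxels, ellipsoid mask in a 40 x 48 x 40 grid, smoothness about 8 mm, 500 replicates, long tail of 60% Gaussian plus 40% exponential (12 mm), two variants of E[n].

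| Correlation shape | Voxel p | A, parametric | B, parametric | B, permutation |
|---|---|---|---|---|
| Gaussian | 0.01 | 6.1% | 1.6-3.6% | 5.0% |
| Gaussian | 0.001 | 3.4% | 2.4-2.6% | 5.4% |
| Long-tailed | 0.01 | 32.9-40.4% | 24.2-32.0% | 3.8% |
| Long-tailed | 0.001 | 12.7-13.9% | 10.4% | 4.8% |

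The Monte Carlo standard error at 5% with 500 replicates is sqrt(0.05 x 0.95 / 500) = 1.0 point. For A's 6.1% it is sqrt(0.061 x 0.939 / 370) = 1.2 points, so that figure is compatible with 5%. A further check in a smaller search volume gave 12% at voxel 0.01 with a long tail. Across all runs the parametric rate at 0.01 is about 2-6% (Gaussian) and about 12-40% (long-tailed); at 0.001 the long-tailed rate is about 9-14%.

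**Step 3: permutation.** Relabelling arms kept the rate within Monte Carlo error of 5% or slightly below it under both shapes and at both thresholds (last column). These runs used 39 relabellings, so rejecting at p <= 0.05 means ranking in the top 2 of 40. Simulation B at 12 v 12, the size at the interim analysis if the arms are balanced, gave 3.4-5.4%.

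**Step 4: sensitivity.** With an assumed focal effect of 0.7 SD (radius 3 voxels, 24 v 24, 300 replicates), detection was:

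| Correlation shape | Parametric 0.01 | Permutation 0.01 | Permutation 0.001 |
|---|---|---|---|
| Gaussian | 29-43% | 51% | 55% |
| Long-tailed | 54-64% | 8% | 38% |

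The long-tailed parametric figure comes from a test whose false-positive rate in the same setting was 24-32%, so it is not a like-for-like benchmark. The 8% shows why the forming threshold should change along with the method.

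**Step 5: error across maps.** If the maps were independent, which is an illustration because they are correlated, 4 maps at 5% each would give 1 - 0.95^4 = 18.5%, and 4 maps at 3 visits 1 - 0.95^12 = 46.0%. Testing both directions at 5% each would give 1 - 0.95^2 = 9.75% per map on the same basis. A per-map permutation test leaves all of these unchanged.

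**The case against.** A reader might infer that the plan's 5% is badly exceeded and that permutation repairs it for nothing. The documents do not support either half.

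- **The method is not visible.** SPM8 is named for the two-sample t-test. The correction is left to the footnoted reference, and it could already be a simulation or permutation method. This stands: parametric inference is the natural reading, but it is an assumption.
- **The excess is conditional.** Under Gaussian correlation there is no clear excess. The high rates appear only with an assumed long tail and move with its shape and the search volume. This stands, and it is why a range is given.
- **Permutation has a price.** It needs no patients or scans, but it can lose sensitivity (Step 4). This stands.
- **Randomisation does not by itself make labels exchangeable.** Section 4 excludes participants who fail an arm-specific cycling trial after assignment, and Section 4f allows removal of those who miss more than 3 sessions. Such losses can differ by arm. This stands as a condition on the remedy. It applies equally to the two-sample t-test.
- **The maps are not central.** Section 4 describes an early phase 1 study built around the connectivity difference between arms, which has its own false-discovery-rate correction. Neither aim in Section 2 names a between-arm map test. This lowers the stakes, but Section 7a still labels parcels primary and Section 7c still claims a corrected 5%.

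**Conclusion.** The point holds in a conditional form, as a low-cost improvement. If the correction is parametric random-field inference, the stated 5% per map at a voxel threshold of 0.01 rests on a spatial correlation shape that the plan does not give: about 2-6% if Gaussian, about 12-40% if long-tailed. A threshold of 0.001 alone reduces the excess without removing it (about 9-14%). These rates illustrate assumed image properties and are not estimates for this trial. The documents do not establish that the 5% will be exceeded here. A label-permutation test held close to 5% in every null setting where it was run, subject to exchangeability of the participants analysed. The two-sided version combined over four maps was not simulated.

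**What to change.** In Section 7c, name the cluster correction and replace the 0.01 threshold and any parametric cluster p-value with the following.

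- A maximum-cluster permutation test of arm labels, for example 5,000 relabellings, with a cluster-forming threshold of 0.001.
- One baseline-to-follow-up change map per participant, with the follow-up visit (week 2 or week 4) fixed in advance. This settles a visit that the section leaves open and should be recorded as a change to the analysis.
- Two-sided family-wise 0.05 over the four maps. Apply each relabelling to all four maps together and refer to the maximum, scaled so that ICA and SCA maps are comparable. The simpler alternative is to test each map at 0.05 / 4 = 0.0125.
- A report, by arm, of exclusions after assignment, with a statement that the test assumes the remaining participants are exchangeable under the null.

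If the footnoted method is already a permutation test, only the method name, threshold, visit, sidedness and handling across maps need adding or justifying.

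The cost is SAP wording, computing time and some sensitivity, with no extra patients or scans. In the assumed long-tailed focal-effect scenario, detection was 38% against 54-64% for the parametric test that does not control its error; adjustment across maps and two-sided testing would lower it further.

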Aim 1. Characterize the baseline time profile of the rsfMRI outcome measures in chronic SCI patients, acquired over 4 weeks of passive (sham) cycling. In order to quantitatively assess the sensitivity of rsfMRI outcome measures to early functional reorganization that occurs in response to FES cycling, baseline time profile of the outcome measures in the absence of the active stimulation must be established. Accordingly, patients will participate in a 4-week passive cycling program. At weeks 0, 2, and 4, sensory and motor network BNC (calculated using ICA- and SCA-derived brain parcels) and ISNCSCI scores will be measured. *Hypothesis: we will observe stable baseline measures of sensory and motor cortex BNC and ISNCSCI scores of the patients during the 4-week passive cycling program, with minimal to no change in values.*

Aim 2. Characterize the time profile of the cortical reorganization in chronic SCI patients that occurs during a 4-week FES cycling program. *Hypothesis: We will observe early sensorimotor cortex BNC changes after 2 weeks of FES cycling, that are predictive of changes in ISNCSCI scores at week 4.* Specifically, we hypothesize that: a) Changes in sensory network BNC at week 2 will correlate with changes in sensory ISNCSCI scores at week 4; b) Changes in motor network BNC at week 2 will correlate with changes in motor ISNCSCI scores at week 4. To test these hypotheses, we will first measure the sensory and motor network BNC and ISNCSCI scores at weeks 0, 2, and 4, then correlate the changes in sensory and motor network BNC at week 2 with the changes in respective ISNCSCI scores at week 4. Finally, longitudinal (pre- and post- intervention) inter- and intra-subject reproducibility of the ICA- and SCA-derived parcels will be assessed.

3. Background (briefly describe pre-clinical and clinical data, current experience with procedures, drug or device, and any other relevant information to justify the research)

Spinal Cord Injury and Rehabilitation.

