Preliminary study: In this preliminary study, we hypothesized that BNC of sensorimotor and visual networks will correlate with the total ISNCSCI score, and performed the study to determine the feasibility of a larger population study. Twelve SCI patients were recruited, and the relationship between the ISNCSCI score and BNC measurements was examined. ISNCSCI sub-scores were first obtained, which were: total upper and lower body motor scores, and total sensory score. The sum of the three scores provided the total ISNCSCI scores. Analysis of the data consisted of preprocessing, PCA, and GICA, and total of 14 intrinsic functional components were identified. BNC between the sensorimotor and visual networks were computed, and plotted against the total ISNCSCI scores. Linear regression analysis was performed to find the best linear fit for the plots. Stronger BNC between the sensorimotor and visual networks was associated with lower total ISNCSCI scores ($R^2=0.35$, $p = 0.04$; [Figure 2](#)[Figure 2](#)). In other words, patients with greater degree of physical impairment tended to have stronger functional connectivity between the sensorimotor and visual networks, suggesting compensatory plastic cortical changes that are related to clinical presentation of the patients. Overall, BNC measures showed good correlations with the total ISNCSCI scores, supporting our hypothesis.

Between network connectivity (BNC) measurements from the above preliminary study provided means, standard deviations, and correlation coefficients for 12 SCI patients. A power analysis¹ revealed that a sample size of 24 subjects will be required to achieve 80% power at an alpha of 0.018; the alpha level was lowered with the correction for multiple comparisons in mind. We will therefore recruit a total of 48 patients. At this point, we do not have enough information about the variability of the BNC in response to the FES to perform a more stringent power analysis. We will use the data in the first 24 SCI subjects recruited to the study to assess the degree of variability in the metric. Based upon these estimates, we will then perform a power analysis to determine how many more subjects will need to be enrolled to assess the significance of our findings.

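### The only BNC that section 7c computes joins sensory to motor parcels, so it cannot separate Aim 2's sensory-network hypothesis from its motor-network hypothesis

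*Combined protocol and SAP*

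**What the plan says.** Section 2 (Objectives, Aim 2) states two hypotheses with different predictors and different outcomes:

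- The sensory hypothesis, labelled (a), reads: "Changes in sensory network BNC at week 2 will correlate with changes in sensory ISNCSCI scores at week 4".
- The motor hypothesis, labelled (b), is its counterpart: "Changes in motor network BNC at week 2 will correlate with changes in motor ISNCSCI scores at week 4".

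Section 7c gives one operational definition of the imaging measure: "The between network connectivity (BNC) between sensory and motor parcels will be calculated using Pearson's correlation coefficient". The plan then describes the correlation as one taken "between pairs of participant specific motor and sensory brain parcels". The correlations are then Fisher-transformed, and "the BNC across groups will be compared using two-sample t tests and adjusted p-values using a false discovery rate correction". The regression that serves Aim 2 follows: "we will investigate whether sensory and motor BNC measured at week 2 of cycling program are related to motor and sensory". Its outcomes are the week-4 ISNCSCI scores, and the model is a multivariate linear regression.

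Elsewhere BNC is defined only in general terms. The primary-outcome table in section 7a calls it "the degree of correlation between two time courses obtained from a pair of brain regions" and names no regions.

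The preliminary study in section 7c used another edge: "BNC between the sensorimotor and visual networks were computed, and plotted against the total ISNCSCI scores". It reports R² = 0.35 and p = 0.04 in 12 patients. The same section says that the pilot BNC measurements supplied the inputs to the power analysis: 24 subjects, 80% power, alpha 0.018.

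**The concern.** Aim 2 needs two variables per participant and visit, one belonging to the sensory network and one to the motor network. The calculation in section 7c yields edges that run from one network to the other. The regression sentence then speaks of sensory and motor BNC as if each had been defined, and neither has.

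What is at stake is the network specificity of the biomarker claim. An analyst who follows section 7c literally has the same type of edge to enter for both hypotheses. An analyst who departs from it must choose edges without a rule, possibly after seeing the data. In either case the trial could not credibly show that sensory-network change anticipates sensory recovery and motor-network change anticipates motor recovery.

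Two mismatches add to this. Section 7c relates values measured at weeks 2 and 4, while Aim 2 specifies changes. The one pilot edge reported, sensorimotor-visual against the total score, appears in neither the Aims nor the planned analysis.

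**Working it through.** **1. Can the specified edge separate (a) from (b)?** Let the sensory parcels be s₁…s_p and the motor parcels m₁…m_q. The edges defined in section 7c are r(sᵢ, mⱼ). Pearson correlation is symmetric, so r(sᵢ, mⱼ) = r(mⱼ, sᵢ), and each edge has one end in each network. Any summary over the whole set, such as its mean, is the same whether labelled sensory or motor. Computing several pairs does not change this, because no rule makes one subset of cross-network edges sensory and another motor.

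**2. Does another section fill the gap?** The abstract and section 7a define BNC generically. Aim 1 and Aim 2 say that sensory and motor network BNC come from ICA- and SCA-derived parcels, but name no partner networks. Nothing supplies the missing definitions.

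**3. Can the planned 24 be reproduced from the pilot edge?** The test, its sidedness and the effect powered are not stated. Assume a test of one correlation at the only reported pilot effect.

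- |r| = √0.35 = 0.592. Check: t = 0.592 × √(10/0.65), 10 df, gives two-sided p = 0.043, in line with the stated 0.04.
- n = ((z_α + z_0.80)/atanh r)² + 3, with atanh 0.592 = 0.680.
- Two-sided: ((2.366 + 0.842)/0.680)² + 3 = 25.2, so 26.
- One-sided: ((2.097 + 0.842)/0.680)² + 3 = 21.7, so 22.
- Regression F test with f² = 0.35/0.65: 23.
- Power at n = 24: 0.77 (two-sided Fisher z), 0.85 (one-sided), 0.84 (F).

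The stated 24 lies within two patients of each result. It is consistent with sizing on the sensorimotor-visual correlation, which is not the same as proof.

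**4. What power would other correlations give?** The documents give no effect for a sensory, motor or sensory-motor edge, so these values of r are assumptions. Power = Φ(atanh r × √21 − 2.366) at n = 24, two-sided alpha 0.018. The required n uses the formula in step 3.

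| Assumed r | Power at n = 24 | n for 80% |
|---|---|---|
| 0.3 | 0.17 | 111 |
| 0.4 | 0.34 | 61 |
| 0.5 | 0.56 | 38 |
| 0.592 (pilot) | 0.77 | 26 |
| 0.7 | Φ(0.867 × 4.583 − 2.366) = Φ(1.61) = 0.95 | (3.207/0.867)² + 3 = 16.7, so 17 |

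The smallest |r| detectable with 80% power at n = 24 is about 0.60. Even for the pilot edge, 12 patients leave a 95% interval of tanh(0.680 ± 1.96/√9), or 0.03 to 0.87, so the whole assumed range is compatible with it.

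**The case against.** The strongest reply is that the authors probably intended several edges. Section 7c speaks of pairs in the plural and applies a false discovery rate correction, and its regression names both sensory and motor BNC. The wording might even be stretched to cover sensory-sensory and motor-motor pairs, though the clause just before it makes that less natural. This stands as a limit: a reader might infer that the predictors of (a) and (b) are one number with correlation 1.0, but the text does not establish that. It does not remove the gap, since intended edges that are not named cannot be analysed as prespecified.

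A reader might also infer that positive results on both hypotheses would be one finding counted twice. That does not follow. Sensory and motor ISNCSCI are different outcomes, and one association can hold without the other. What is lost is network specificity.

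On power, a reader might take it as fact that the trial was sized on an edge it will not analyse. Section 7c mentions means, standard deviations and correlation coefficients from a pilot with 14 components, and never says which effect was used. The link is an inference. The plan also admits that BNC variability in response to FES is unknown and schedules a new power analysis after 24 subjects. That softens the power issue, but the re-estimation itself needs a defined metric, and under section 7d it can lead to discontinuation if more than 50 subjects are required.

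Finally, section 4a gives the trial's purpose as comparing BNC change between FES and passive cycling, and a sensory-motor edge is usable for that. This is correct and confines the point to Aim 2.

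**Conclusion.** The point holds for Aim 2. The only BNC specified in section 7c cannot distinguish hypothesis (a) from (b), and the sensory and motor BNC in the regression have no separate definitions. The use of measured values in place of changes is a second mismatch with Aim 2. These conclusions rest on the text and on the symmetry of a correlation, with no numerical assumption.

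The power part is weaker. The 80% at 24 subjects rests on pilot BNC data and has not been shown for the Aim 2 predictors. That the sensorimotor-visual edge sized the trial is an inference, supported by n = 24 falling within the 22 to 26 that R² = 0.35 implies. The true power could be well below or above 80%: 17% at r = 0.3 and 95% at r = 0.7, both assumed. The between-group comparison of BNC is not affected by this point.

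**What to change.** In section 7c, before outcome data are seen:

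1. Define two distinct predictors per participant and visit, a sensory-network BNC and a motor-network BNC, by naming the parcel pairs or partner networks for each. Possible forms are the mean Fisher z to a fixed set of partner networks, or within-domain pairs. The choice is the sponsor's, provided that the two differ and are fixed in advance.
2. Enter their baseline-to-week-2 changes in (a) and (b) against the baseline-to-week-4 changes in the matching ISNCSCI sub-scores.
3. Report the sensory-motor edge under its own name.
4. Base the planned re-estimation after 24 subjects on these Aim 2 predictors.
5. State that the 80% power at 24 subjects rests on pilot BNC data and has not been shown for these predictors.

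The cost is SAP wording and a few extra correlations from scans already in the plan. No new data and no added participant burden are needed.
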